3.0 ANALYSIS

3.1 Analysis Methods

The primary and secondary analyses will be conducted following intention-to-treat (ITT) principles, ensuring that participants are analyzed in their originally assigned treatment groups, regardless of adherence or protocol deviations. The date on which the participant's fracture(s) occurred will be used as the starting point for all time-to-event analyses.

We will use multiple imputations to account for missing data in the analyses and minimize potential bias under the assumption that the data are missing at random (MAR). This approach will allow for the uncertainty associated with missing values to be properly accounted for, improving the robustness of statistical inferences.⁴ Additionally, as we anticipate high rates of early withdrawal, we will account for this in the analyses, if needed.

If any of the analysis models fail to converge, we will remove adjustment covariates one by one until convergence is achieved. The same set of covariates will be used consistently across all models in the primary and secondary analyses.

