3.1.2 Secondary Analyses

- 1) *Health-Related Quality of Life (HRQoL)*: We will use linear repeated measures mixed modeling to explore the association between: 1) CBT treatment status and Short Form-36 (SF-36) Physical Component Summary (PCS) scores over 12 months, and 2) CBT treatment status and SF-36 Mental Component Summary (MCS) scores over 12 months. The SF-36 is an established, reliable and validated health status measure.⁵⁻⁷ It measures HRQoL through an 8-domain profile of functional health and well-being, physical and mental health summary measures (PCS and MCS). The SF-36 PCS and MCS are scored on a scale from 0 to 100, with 100 representing the highest level of functioning possible. SF-36 PCS and MCS scores will be included as the dependent variable in each corresponding model. CBT treatment status, stratification variables, and time of assessment (continuous measure in days) will be included in the models as fixed effects, with patients entered as a random intercept. The models will also be adjusted for baseline SF-36 PCS and MCS scores, accordingly, as well as including a time-by-treatment interaction term. Results will be reported using marginal standardization as adjusted mean differences (aMDs) with 95% CIs and p-values (**Table 8**).
- 2) *Return to Function*: We will use Cox proportional hazards regression modeling to explore the association between: 1) CBT treatment status and returning to $\geq 80\%$ of pre-injury functioning, 2) CBT treatment status and returning to full function with respect to work, 3) CBT treatment status and returning to full function with respect to leisure activities, and 4) CBT treatment status and returning to full function with respect to responsibilities around the home. These return to function components are measured using the Return to Function questionnaire, which has been used in a previous fracture trial⁸ documents when participants return to work, household activities, and leisure activities without limitations, as well as when they achieve 80% of their pre-injury function. Participants will be censored at their last documented follow-up visit. The analyses will adjust for stratification variables and the results will be reported as hazard ratios (HRs) with 95% CIs and p-values (**Table 9**).

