Table 12: Sensitivity Analysis of the Impact of CBT versus Usual Care on Primary and Secondary Outcomes Using Available Case Analysis

Outcome	CBT n (%) (n= XX)	Usual Care n (%) (n= XX)	Estimate** (95% CI)	p-value
Primary Outcome				
Moderate to Severe ($\geq 4/10$) PPSP, adjusted mean (95% CI)				
Secondary Outcomes				
SF-36 PCS, mean (95% CI)				
SF-36 MCS, mean (95% CI)				
BPI-SF Average Pain Severity Score, mean (95% CI)				
BPI-SF Pain Interference Score, mean (95% CI)				
Taking an opioid class medication (6 months)				
Taking an opioid class medication (12 months)				

**Estimates are presented as an adjusted risk ratio for the primary outcome, as an odds ratio for the opioid use outcome, and as adjusted mean differences for the remainder of the secondary outcomes.

Table 13: Treatment-Related Serious Adverse Events and Fracture-Related Complications*

Category	CBT n (%) (n= XX)	Usual Care n (%) (n= XX)
Serious adverse event		
Fracture-related complication		
Wound healing problem		
Compartment syndrome		
Superficial infection		
Deep/Organ/Space infection		
Delayed union		
Nonunion		
Malunion		
Implant failure/breakage		
Dislocation/instability		
Heterotopic ossification		
Osteolysis		
Avascular necrosis		
Pain (not otherwise covered)		
Other		

*This table shows all response options for the data collected. In the primary manuscript, some data categories may be collapsed as appropriate or presented in a supplementary appendix.

SUPPLEMENTARY TABLES

Table S1: Open Fracture Characteristics

	CBT n (%) (n= XX open fractures)	Usual Care n (%) (n= XX open fractures)
Gustilo classification I II IIIA IIIB IIIC		
Skin Laceration with edges that approximate Laceration with edges that do not approximate Laceration associated with extensive degloving		
Muscle No appreciable muscle necrosis, some muscle injury with intact muscle function Loss of muscle but the muscle remains functional, some localized necrosis in the zone of injury that requires excision, intact muscle-tendon unit Dead muscle, loss of muscle function, partial or complete compartment excision, complete disruption of a muscle-tendon unit, muscle defect does not reapproximate		
Arterial No major vessel disruption Vessel injury without distal ischemia Vessel injury with distal ischemia		

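### The four return-to-function Cox models rely on plain censoring with stratification covariates only, and nothing in the plan ties the anticipated withdrawal to these event times or tests the assumption

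*SAP*

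**What the plan says.** SAP section 3.1.2 item 2 introduces the models thus: "We will use Cox proportional hazards regression modeling to explore the association between: 1) CBT treatment status and returning to", followed by four endpoints: at least 80% of pre-injury function, work, leisure and home responsibilities. The handling of incomplete follow-up and the covariates are fixed together: "Participants will be censored at their last documented follow-up visit. The analyses will adjust for stratification variables". Section 3.1.1 lists the stratification variables as clinical site, sex, any open fracture and SPOC band.

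Section 3.1 sets the general missing-data approach: "We will use multiple imputations to account for missing data in the analyses", under missing at random. It adds: "as we anticipate high rates of early withdrawal, we will account for this in the analyses, if needed". It gives no rate, method, trigger or variables, and does not mention censored event times.

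The check on missing data is Table 12, "Sensitivity Analysis of the Impact of CBT versus Usual Care on Primary and Secondary Outcomes Using Available Case Analysis". Its seven rows are moderate to severe PPSP, SF-36 PCS and MCS, two BPI-SF scores, and opioid use at 6 and 12 months. It has no return-to-function row. Table 11 covers PPSP only.

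Baseline SF-36 and BPI-SF scores are covariates in their own mixed models (section 3.1.2 items 1 and 3), and Table 7 lists both forms at 3, 6, 9 and 12 months.

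**The concern.** A participant who leaves follow-up becomes a censored record at the last visit. The Cox model then treats those still followed in that arm, with the same site, sex, fracture type and SPOC band, as representative of the person who left. Pain and function plausibly predict recovery and may predict leaving, yet the Cox models use no pain or function score.

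Censoring at last contact is in effect the available-case analysis of an event time. For the other secondary outcomes the plan makes available-case analysis the sensitivity check and imputation the main method. For these four, the available-case method is the main analysis and nothing stands beside it. They are 4 of 10 secondary results (2 SF-36 + 4 return to function + 2 BPI-SF + 2 opioid), and faster return to function is a named secondary objective. If the assumption fails differently in the two arms, the hazard ratio is biased and the planned output would not show it.

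**Working it through.** The SAP gives no withdrawal rate, event count or power for these models and refers elsewhere for sample size, so there is no stated figure to reproduce. The question is how far a true hazard ratio of 1 moves under the planned analysis.

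**From the SAP:** visits at 3, 6, 9 and 12 months; censoring at the last visit; SPOC in three bands as a covariate.

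**Assumed:**
- One pain/function score X (SD 1, higher is worse), changing between visits as X(next) = 0.8·X + 0.6·noise.
- Hazard of return per month = 0.12·exp(−b·X), with b = 0.5, or 0.8 for stronger prognosis. There is no treatment effect.
- SPOC band from a latent score correlated 0.4 with X, cut at ±0.43.
- Probability of leaving, at baseline and after each of the first three visits, = 1/(1 + exp(−(a + g·X))), with a and g set by arm.

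Site, sex and open fracture were not simulated.

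**Three Cox fits:** (i) planned: arm and SPOC band; (ii) the same plus baseline X; (iii) inverse-probability-of-censoring weights, the product over visits of P(stay | arm, SPOC) / P(stay | arm, SPOC, X, X×arm).

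Results with 200,000 per arm (usual care / CBT; a hazard ratio above 1 favours CBT; Monte Carlo SE about 0.003):

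| Pattern | a | g | % leaving | (i) planned | (ii) baseline | (iii) weights |
|---|---|---|---|---|---|---|
| No withdrawal | −9 / −9 | 0 / 0 | 0 / 0 | 0.996 | 0.997 | 0.996 |
| Same in both arms | −2.0 / −2.0 | 0.7 / 0.7 | 29.8 / 29.6 | 1.000 | 0.999 | 0.999 |
| More loss on CBT, same slope | −2.6 / −1.8 | 0.7 / 0.7 | 19.6 / 33.8 | 1.034 | 1.009 | 1.003 |
| More loss on CBT, X-dependent on CBT only | −2.6 / −1.8 | 0 / 0.7 | 16.0 / 33.8 | 1.068 | 1.013 | 1.000 |
| As above, b = 0.8 | −2.6 / −1.8 | 0 / 0.7 | 15.8 / 33.9 | 1.091 | 1.013 | 0.993 |
| Similar loss, X-dependent on CBT only | −2.0 / −2.1 | 0 / 0.7 | 26.4 / 27.9 | 1.056 | 1.011 | 1.001 |
| Milder dependence on CBT only | −2.3 / −1.9 | 0 / 0.4 | 20.5 / 29.7 | 1.038 | 1.011 | 1.001 |
| As above, b = 0.8 | −2.3 / −1.9 | 0 / 0.4 | 20.3 / 29.7 | 1.055 | 1.016 | 1.004 |
| Better-off leave CBT | −2.0 / −2.1 | 0 / −0.7 | 26.3 / 25.8 | 0.948 | 0.987 | 0.998 |
| Worse-off leave usual care | −2.1 / −2.0 | 0.7 / 0 | 28.0 / 26.3 | 0.947 | 0.990 | 0.999 |

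False results favouring CBT (planned model, b = 0.5, 500 per arm assumed, 600 replicates, nominal 2.5%, Monte Carlo SE about 1 point):
- No withdrawal: 1.8%.
- Same pattern in both arms: 2.7%.
- 30% against 20% leaving, slope 0.4 on CBT only: 5.2%.
- 34% against 16% leaving, slope 0.7 on CBT only: 11.3%.

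Three things follow. Withdrawal that depends on X does no harm if the pattern is the same in both arms. Equal totals do not protect if the dependence differs by arm. The sign follows which participants leave which arm. The weights were correctly specified by construction, so column (iii) is a best case.

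**The case against.** A reader might infer that the plan biases these hazard ratios in favour of CBT. The documents do not support that. The SAP does not say that pain or function drives withdrawal, or that withdrawal differs by arm. With the same pattern in both arms the estimate is about 1.00, and two plausible patterns push it to about 0.95, against CBT.

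It is also tempting to treat dropping out of CBT as the mechanism. A footnote to Figure 1 says follow-up assessments took place however many sessions a participant had completed, so stopping CBT is not itself censoring. Part of the early withdrawal anticipated in section 3.1 may be of that kind.

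Four further objections carry some weight:
- Section 3.1 does not exclude the Cox models from imputation and leaves room to account for withdrawal. That is fair, but without a method, a trigger or a link to event times, the decision would be taken after the data are seen.
- SPOC band may already carry part of the prognosis. The simulation includes it, at an assumed correlation, and bias remains.
- The primary and opioid models also omit baseline pain and function, and the SF-36 and BPI-SF models each use only their own baseline. The Cox covariates are therefore not out of line with the rest of the plan. The case for adding scores rests on the censoring assumption, not on consistency.
- Time runs from the fracture date, while patients are approached 2 to 12 weeks later, so the baseline scores postdate time zero. They remain usable covariates if taken before treatment starts, but the SAP should say so.

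**Conclusion.** The concern holds as a specification gap in four secondary outcomes. The models are valid only under an independence assumption that the plan neither states nor tests, in a trial that expects high withdrawal. The plausible size is modest: a null hazard ratio of about 0.95 to 1.09 in the scenarios tried, in either direction, and about 1.00 if loss follows the same pattern in both arms. At an assumed 500 per arm, the less favourable scenarios raised false results favouring CBT from a nominal 2.5% to between 5.2% and 11.3%. These figures rest on assumed withdrawal rates, slopes, prognostic strength and sample size. They show what can happen, not what will. Where plain censoring gave 1.03 to 1.09, baseline adjustment gave 1.01 to 1.02 and weighting 0.99 to 1.00. In the two reverse patterns they gave 0.99 and 1.00. The primary outcome is not affected.

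**What to change.** In SAP section 3.1.2 item 2:

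(a) Add baseline SF-36 PCS and baseline BPI-SF Pain Interference as covariates in the four Cox models.

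(b) Add a sensitivity analysis for each of the four outcomes: a Cox model with inverse-probability-of-censoring weights, estimated within arm from the last completed BPI-SF and SF-36 PCS. Report it in a separate table, or retitle Table 12, since its present title covers only available-case analysis.

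(c) State that the multiple imputation in section 3.1 does not apply to these event times.

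Section 3.1 also asks for one covariate set across all primary and secondary models. Its wording should allow for outcome-specific baseline scores, which the SF-36 and BPI-SF models already use.

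The cost is SAP wording and modest programming, with no new data. The hazard ratio becomes conditional on two more covariates, and the weighted confidence intervals will be somewhat wider. Neither step deals with withdrawal driven by changes that no completed form recorded.

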3.2 Subgroup Analyses

To explore for treatment effect heterogeneity on trial outcomes, we will use the same analytical approach as specified for the primary outcome above but include a treatment by subgroup interaction term in the model. If we have enough participants to conduct reliable subgroup analyses, we will report results by the prespecified subgroups, which consist of: (1) sex (indicated as male or female), (2) the presence or absence of an eligible open fracture, (3) veteran/military/first responder status (as self-reported by the participant), (4) SPOC Scores (categorized into tertiles), and (5) site location (Canada or United States). Prior conducting the final analysis, site location (Canada or the United States) was added as a subgroup analysis to assess its potential role as an effect modifier.

For the sub-group analysis, SPOC scores will be analysed according to tertiles, as several other analyses suggest that the relationship with outcomes is not completely linear. If the numbers do not support subgroup analysis with SPOC scores as three categories, a binary threshold will be considered.

Subgroup results will be reported using marginal standardization and stratified by the subgroup as aRRs with 95% CIs, p-values, and the interaction p-values in a forest plot and table (**Table 10**). These analyses will be approached and reported in accordance with best practices and guidelines for subgroup analyses.^{10–14} For subgroup effects that show a statistically significant test of interaction ($p \leq 0.05$), we will use ICEMAN criteria to guide inferences about the credibility of our subgroup analyses.¹⁴

Subgroup Analyses Overview

Objective	Hypothesis
Subgroup Analysis 1	
Males versus females	CBT will be associated with a larger reduction in the prevalence of PPSP in females compared to males.
Subgroup Analysis 2	
Any open fracture versus no open fracture	CBT will be associated with a larger reduction in the prevalence of PPSP in participants with open fractures compared to participants with only closed fractures.
Subgroup Analysis 3	
Military, veteran, and first responders versus other patients	CBT will be associated with a larger reduction in the prevalence of PPSP in participants who are employed by the military, veterans, or first responders.
Subgroup Analysis 4	
Higher versus medium versus lower SPOC scores	CBT will be associated with a larger reduction in the prevalence of PPSP in participants with higher SPOC scores.
Subgroup Analysis 5	
Site location (Canada versus the United States)	CBT will be associated with a larger reduction in the prevalence of PPSP in participants from sites located in Canada.

3.3 Sensitivity and Exploratory Analyses

We will conduct the following additional analyses to explore the robustness of our findings:

1. Assess if CBT, versus usual care, reduces the prevalence of any severity of PPSP over 12-months post-fracture (**Table 11**).
2. A sensitivity analysis limited to the primary outcome to compare those participants randomized to the CBT intervention at the primary site, defined as the site with the highest enrollment (**Table 11**).
3. Assess the primary outcome in only those participants randomized to the CBT intervention who fully adhered to: 1) at least three CBT modules and 2) at least six CBT modules (**Table 11**), limiting data to the primary site only, defined as the highest enrolling site.
4. Assess if CBT, versus usual care, reduces the prevalence of PPSP severity over 12-months post-fracture using available case analysis (**Table 12**).

These analyses will help determine whether greater engagement with CBT is associated with improved outcomes. The exploratory and sensitivity analyses will follow the same analysis methods as described for the primary outcome, including appropriate regression models and adjustments for stratification variables.

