Outcome	CBT n (%) (n= XX)	Usual Care n (%) (n= XX)	Estimate** (95% CI)	p-value
Primary Outcome				
Moderate to Severe ($\geq 4/10$) PPSP, adjusted percent (95% CI)				
Secondary Outcomes				
SF-36 PCS, mean (95% CI)				
SF-36 MCS, mean (95% CI)				
BPI-SF Average Pain Severity Score, mean (95% CI)				
BPI-SF Pain Interference Score, mean (95% CI)				
Taking an opioid class medication (6 months)				
Taking an opioid class medication (12 months)				

**Estimates are presented as an adjusted risk ratio for the primary outcome, as an odds ratio for the opioid use outcome, and as adjusted mean differences for the remainder of the secondary outcomes.

Table 9: Impact of CBT versus Usual Care on Return to Pre-Injury Function, Work, and Activities

Function Category	Hazard Ratio (95% CI)	p-value
≥80% of Pre-injury Functioning CBT vs. No CBT		
Work* CBT vs. No CBT		
Leisure Activities CBT vs. No CBT		
Responsibilities around the Home CBT vs. No CBT		

*Unemployed participants were excluded from analyses

Table 10: Impact of CBT versus Usual Care on Moderate to Severe PPSP in Different Subgroups

Subgroup	CBT Adjusted percent (95% CI) (n= XX)	Usual Care Adjusted percent (95% CI) (n= XX)	Adjusted Risk Ratio (95% CI)	p-value
Sex				
Male				
Female				
Fracture Type				
Any open fracture				
No open fracture				
Background/Employment				
Military, veteran, and first responder				
Not a veteran, first responder or employed by the military				
SPOC Score				
Low (≤ 58)				
Medium ($58 < \text{SPOC score} \leq 85$)				
High (>85)				
Site Location				
Canada				
United States				

Table 11: Sensitivity and Exploratory Analyses

Outcome	CBT Adjusted percent (95% CI) (n= XX)	Usual Care Adjusted percent (95% CI) (n= XX)	Adjusted Risk Ratio (95% CI)	p-value
Exploratory Outcome – Any Severity of PPSP				
PPSP Severity Any severity ($\geq 1/10$)				
Primary Outcome - Participants randomized to the CBT intervention at the primary site				
PPSP Severity Moderate to Severe ($\geq 4/10$)				
Primary Outcome – Adherence to at least three CBT modules at the primary site				
PPSP Severity Moderate to Severe ($\geq 4/10$)				
Primary Outcome – Adherence to at least six CBT modules at the primary site				
PPSP Severity Moderate to Severe ($\geq 4/10$)				

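### The module-completer analyses set a self-selected part of the CBT arm against all of usual care, so their risk ratios mix any CBT effect with who completes therapy

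*SAP*

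**What the plan says.** SAP section 3.3 lists four sensitivity and exploratory analyses. Item 3 is to "Assess the primary outcome in only those participants randomized to the CBT intervention who fully adhered to" at least three modules and, separately, at least six, "limiting data to the primary site only, defined as the highest enrolling site". Table 11 gives each threshold a row with a CBT column, a usual-care column, an adjusted risk ratio and a p-value. Nothing restricts the usual-care column by adherence.

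The section applies the primary-outcome methods, "including appropriate regression models and adjustments for stratification variables". Section 3.1.1 names those variables: clinical site, sex, open fracture and SPOC category. The section then states its purpose: "These analyses will help determine whether greater engagement with CBT is associated with improved outcomes".

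Item 2 is "to compare those participants randomized to the CBT intervention at the primary site". Its Table 11 row reads "Primary Outcome - Participants randomized to the CBT intervention at the primary site". Neither says which usual-care participants form the comparison.

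**The concern.** Module completion happens after randomisation and can be observed only in the CBT arm. Item 3 removes the non-completers from that arm. Their counterparts in usual care cannot be identified and so remain. The two groups are then no longer balanced by randomisation, and the risk ratio answers two questions at once: what CBT did, and how completers would have fared anyway.

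Nor is the contrast a comparison of more engagement with less. It compares the engaged part of one arm with the whole of the other, so it does not directly support the inference about engagement that the section draws. Section 3.1 expects early withdrawal to be common. If that includes stopping CBT, the completers could be well short of the full arm. A risk ratio with a p-value and no caveat could then be read as evidence of efficacy.

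**Working it through.** **Inputs.** From the SAP: the cuts at three and six modules, seven modules in all (section 2.3), unselected usual care in Table 11, and adjustment for stratification variables only. The SAP gives no completion rate, pain risk or sample size, so there is no plan figure to reproduce. All risks and shares below are assumptions.

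**Step 1: the ratio when CBT does nothing.** Let *p* be the usual-care risk of moderate to severe pain, *f* the share of the CBT arm that completes, and *p_c* and *p_n* the risks in completers and non-completers. With no effect, randomisation gives both arms the same overall risk:

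p = f·p_c + (1 − f)·p_n, so p_n = (p − f·p_c)/(1 − f)

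The item 3 contrast then tends to p_c/p. For f below 1, this equals 1 only if p_c = p_n. With p = 0.35:

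- f = 0.50, p_c = 0.28: p_n = (0.35 − 0.14)/0.50 = 0.42; ratio 0.28/0.35 = 0.80.
- f = 0.30, p_c = 0.25: p_n = (0.35 − 0.075)/0.70 = 0.39; ratio 0.25/0.35 = 0.71.
- f = 0.60, p_c = 0.31: p_n = (0.35 − 0.186)/0.40 = 0.41; ratio 0.31/0.35 = 0.89.
- Opposite direction, f = 0.50, p_c = 0.42: p_n = (0.35 − 0.21)/0.50 = 0.28; ratio 0.42/0.35 = 1.20.

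**Step 2: a wider range.** With r = p_c/p_n, the null ratio is r/(f·r + 1 − f), which does not depend on *p*. For f from 0.30 to 0.70:

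- r = 0.90: 0.93 to 0.97
- r = 0.75: 0.81 to 0.91
- r = 0.60: 0.68 to 0.83

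**Step 3: chance of a significant false benefit.** This uses a two-sided 5% comparison of two proportions, so 2.5% is nominal in the direction of benefit. Take p = 0.40 and f = 0.50.

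- r = 0.60 (completers 0.30, non-completers 0.50, ratio 0.75): 22% with 100 randomised per arm at the site, 39% with 200.
- r = 0.90 (ratio 0.95): 4.3% and 5.3%.

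**Step 4: does the adjustment repair it?** Within one site, clinical site is constant and adjusts for nothing. Sex, open fracture and SPOC category remain. They can remove the part of the selection that they explain, so r is best read as the ratio left after adjustment. Section 2.3 also tabulates compliance by age and Injury Severity Score, and neither is in the model. Motivation and early recovery are not in it either.

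**Step 5: an estimate that keeps the randomised comparison.** A complier-average effect on the risk-difference scale is the difference between arms as randomised, divided by the share who receive CBT (assuming none do in usual care). Under the first null case it is (0.35 − 0.35)/0.50 = 0, whatever the prognosis of completers. Its standard error is roughly 1/f times that of the intention-to-treat difference: 1/0.70 = 1.4, 1/0.50 = 2 or 1/0.30 = 3.3.

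**Step 6: item 2.** If both arms are restricted to the primary site, the comparison is randomised. The other reading sets CBT at that site against usual care at all sites. It was simulated with no effect: 300 trials per scenario, ten sites, four visits, and a log-link Poisson model with patient-clustered variance standing in for the mixed log-binomial model.

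- Site in the model: the ratio averaged over visits was 0.996 (false benefit 3.3%) when the primary site had lower risk (0.30 against 0.40), and 0.987 (2.3%) when only its time course differed. In the latter case the 12-month ratio drifted to 0.86.
- Site dropped: 0.81 (73%) and 0.79 (91%).

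**The case against.** The case for leaving item 3 alone is that it is exploratory, that the primary and secondary analyses follow intention to treat, and that the SAP speaks of association. It also plans to describe how early stoppers differ at baseline (section 2.2) and to tabulate compliance by baseline factors (section 2.3, Tables 5 and 6). All of this is true and limits the damage. The descriptions tell a reader who the completers are, but they do not remove the selection from the risk ratio, and no label in section 3.3 or Table 11 warns that the comparison is not randomised.

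Four stronger readings are tempting and not supported:

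- **That the bias must favour CBT.** The SAP says nothing about prognosis by adherence. If people with more pain keep going, the ratio is pushed above 1.
- **That the SAP claims a causal effect of engagement.** Its word is association.
- **That item 2 is biased in the same way.** The natural reading restricts both arms. Even with usual care from all sites, the planned fixed effect for site keeps the average ratio near 1. Marked bias in that average appears if site is also removed under the non-convergence rule in section 3.1, which gives no order for dropping covariates.
- **That limiting item 3 to one site is an error.** It is a stated choice that costs precision.

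**Conclusion.** The point holds for item 3. Followed as written, it yields a selection-biased contrast whose risk ratio departs from 1 under no effect whenever completers and non-completers differ in prognosis after adjustment. Where completers have the better prognosis, the illustrations run from 0.71 to 0.89, and the wider grid from 0.68 to 0.97; the mirror-image case gives 1.20. These sizes rest wholly on assumed risks and completion shares. The direction cannot be known from the SAP.

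The primary intention-to-treat result stands untouched, so this is a change that should be made to an exploratory analysis and not a threat to the trial's main conclusion. For item 2 the defect is an unstated comparator, to be closed by wording.

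**What to change.** 1. Replace item 3 with, or make it secondary to, a complier-average causal effect in all randomised participants of the intention-to-treat analysis, with assignment as the instrument and the same covariates.
2. Define receipt as any module started or completed. A cut at three or at six assumes that fewer modules do nothing, which strains the exclusion restriction at either threshold. The SAP's tables count completed modules only, so check whether starts are recorded. The alternative is an instrumental-variable effect per module, with its linearity assumption stated.
3. If the completer contrast is kept, label it in section 3.3 and Table 11 as a non-randomised comparison, and delete the sentence on engagement and improved outcomes.
4. In item 2 and its Table 11 row, state that both arms are restricted to the primary site.

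Items 3 and 4 cost only wording. Items 1 and 2 cost wider confidence intervals (step 5), reliance on the exclusion restriction, which the report should state, and some programming, because the outcome is repeated, binary and multiply imputed. The changes should be made before results by arm are known.

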3.1.1 Primary Analysis

We will use a mixed effects log-binomial model to determine the association between CBT treatment and moderate to severe PPSP (score of $\geq 4/10$) over 12 months post-fracture. The choice of using a PPSP score of $\geq 4/10$ for the primary analysis was based on scores of less than 4 being defined as 'mild' pain, and so less important to patients. Prevalence of moderate to severe PPSP will be our dependent variable. Only the highest PPSP score at each visit will be included for participants with multiple fractures. CBT treatment status, stratification variables (clinical site, sex, at least one open fracture versus no open fracture(s), and high illness beliefs [defined as Somatic Pre-Occupation and Coping [SPOC] score > 85] or medium illness beliefs [$58 < \text{SPOC score} \leq 85$] versus low illness beliefs [$\text{SPOC score} \leq 58$]), and time of assessment (continuous measure in days) will be included in the model as fixed effects, with patients entered as a random intercept. A time-by-treatment interaction term will also be added to the model, allowing the

treatment effect to vary over time. Results will be reported using marginal standardization as adjusted risk ratios (aRRs) with a 95% confidence interval (95% CI) and p-value (**Table 8**).

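### The plan expects much early withdrawal and imputes under missing at random, but its only missing-data sensitivity analysis does not relax that assumption

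*SAP*

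**What the plan says.** Section 3.1 of the SAP uses multiple imputation "under the assumption that the data are missing at random (MAR"). It then adds: "as we anticipate high rates of early withdrawal, we will account for this in the analyses, if needed". It gives no expected rate, method or trigger, and does not define early withdrawal.

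The primary model is in section 3.1.1: "We will use a mixed effects log-binomial model to determine the association between CBT treatment and moderate to severe PPSP". It has a random patient intercept, the stratification variables, time and a time-by-treatment term.

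Section 3.3 lists four further analyses intended to examine robustness: PPSP of any severity; the highest-enrolling site only; CBT participants at that site who completed three or more, or six or more, modules; and "Assess if CBT, versus usual care, reduces the prevalence of PPSP severity over 12-months post-fracture using available case analysis". Only the last concerns missing data. Its output, Table 12, is titled "Sensitivity Analysis of the Impact of CBT versus Usual Care on Primary and Secondary Outcomes Using Available Case Analysis". On the model, section 3.3 says: "The exploratory and sensitivity analyses will follow the same analysis methods as described for the primary outcome".

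Two other places matter. Section 2.2 plans a baseline comparison of participants who left the CBT programme early with those who did not. A footnote to Figure 1 in section 4.0 says that follow-up assessments took place however many sessions a participant had completed.

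**The concern.** A missing-data sensitivity analysis should vary the assumption that the main result depends on. Here that assumption is MAR: given the observed data and the variables in the model, the chance that an outcome is missing does not depend on its value. In a pain trial it could fail in either direction. People who do badly may give up on follow-up, and so may people who have recovered.

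If the one planned check also relies on MAR, a matching result in Table 12 may be reported as robustness when the main untestable assumption has not been examined. The promise to account for withdrawal if needed does not fill the gap, because it leaves both the decision and the method open until the data have been seen.

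**Working it through.** **Step 1. What each analysis assumes.**

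| Analysis | Source in SAP | Assumption about missing outcomes |
|---|---|---|
| Primary: multiple imputation | 3.1, 3.1.1 | MAR given the variables in the imputation model (not listed) |
| Available case, PPSP, SF-36 and BPI-SF | 3.3 item 4, Table 12 | MAR given model covariates and the participant's observed visits, if fitted by likelihood |
| Available case, opioid use at 6 and 12 months | 3.1.2 item 4, Table 12 | Missingness unrelated to the outcome given treatment and stratification variables; no other visits are used, so at least as strict |

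No row lets missingness depend on the unseen outcome. The other three analyses in section 3.3 change the outcome threshold or the population, not the missing-data assumption. The SAP contains no delta-adjusted, pattern-mixture, reference-based, tipping-point or worst-case analysis.

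**Step 2. How much an unexamined departure could matter.** The SAP gives no event rate, dropout rate or sample size, so there is no figure to reproduce and every input here is an assumption. Observed prevalence of moderate-to-severe PPSP is taken as 28% on CBT and 35% on usual care, so the risk ratio (RR) under MAR is 0.28/0.35 = 0.80. Let m be the share of outcomes missing and d the excess risk among missing outcomes over what MAR predicts.

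- Shift in CBT only: RR = (0.28 + m·d)/0.35
- Same m and d in both arms: RR = (0.28 + m·d)/(0.35 + m·d)

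| m | d | CBT only | Both arms |
|---|---|---|---|
| 25% | 5 points | 0.2925/0.35 = 0.84 | 0.2925/0.3625 = 0.81 |
| 25% | 10 points | 0.305/0.35 = 0.87 | 0.305/0.375 = 0.81 |
| 25% | 15 points | 0.3175/0.35 = 0.91 | 0.3175/0.3875 = 0.82 |
| 35% | 5 points | 0.2975/0.35 = 0.85 | 0.2975/0.3675 = 0.81 |
| 35% | 10 points | 0.315/0.35 = 0.90 | 0.315/0.385 = 0.82 |
| 35% | 15 points | 0.3325/0.35 = 0.95 | 0.3325/0.4025 = 0.83 |

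A shift in usual care alone moves the RR the other way: with m = 25% and d = 10 points, 0.28/0.375 = 0.75.

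**Step 3. Tipping point on the same inputs.** With a CBT-only shift, RR = 1 needs m·d = 0.07. That is d = 28 points at 25% missing (risk 56% among missing CBT outcomes) and d = 20 points at 35% missing (risk 48%).

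**Step 4. A second set of assumed inputs.** Take 32% against 40% (again RR 0.80) and let missing CBT outcomes carry k times the observed CBT risk, with usual care at MAR. Then RR = 0.80 × (1 − m + m·k).

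| CBT missing | k = 1.25 | k = 1.5 | k = 2 | k at which RR = 1 |
|---|---|---|---|---|
| 10% | 0.82 | 0.84 | 0.88 | 3.5 (not attainable: 3.5 × 32% exceeds 100%) |
| 20% | 0.84 | 0.88 | 0.96 | 2.25 |
| 30% | 0.86 | 0.92 | 1.04 | 1.83 |
| 40% | 0.88 | 0.96 | 1.12 | 1.62 |

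The result is sensitive when the departure differs between arms and much is missing. It is not sensitive when the departure is alike in both arms.

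**The case against.** The SAP states its MAR assumption openly and never claims that Table 12 tests departures from it. It also reports losses with reasons and completion rates by visit. Three stronger readings are tempting, and the document supports none of them.

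- **A reader might infer that the imputed and available-case results must agree.** They need not. The imputation model is unspecified and could use variables outside the analysis model. Participants with no follow-up visit are imputed in one analysis and contribute no outcome in the other. Table 12 is therefore a fair check on dependence on the imputation, but agreement would not rule out outcome-dependent dropout.
- **A reader might infer that dropout is driven by CBT and will be higher in that arm.** The SAP does not say so. Early withdrawal is undefined, section 2.2 speaks only of leaving the programme, and the Figure 1 footnote means that stopping modules does not by itself create missing outcomes. The sentence does follow directly on the missing-data text, so leaving follow-up is a plausible reading, but it is not established.
- **A reader might infer that a favourable result would be overturned.** None of the 28%/35% scenarios in step 2 reaches RR 1, and nearly all the movement there comes from shifting CBT alone. The formulas also treat the missing share as if every visit were lost. With visits at 3, 6, 9 and 12 months, a late leaver keeps earlier data, so the effective m is smaller.

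These objections limit the size of the point. They do not supply an analysis that relaxes MAR.

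**Conclusion.** The point holds as a gap in the sensitivity analyses, not as an error in the primary analysis. The plan expects substantial withdrawal and relies on MAR, and its one missing-data check needs MAR or a condition at least as strict. Agreement between the two would say nothing about robustness to outcome-dependent dropout.

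The size cannot be determined from the SAP. On the assumed 28% and 35%, the RR of 0.80 moves to between 0.84 and 0.95 for a CBT-only shift of 5 to 15 points with 25% to 35% missing, and only to about 0.81 to 0.83 when both arms share the shift and the missing share. Whether the trial is nearer the first case or the second is what a properly specified sensitivity analysis would explore. The change is worth making because it is cheap and because the wording on withdrawal now leaves a choice open until the data are seen.

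**What to change.** Keep Table 12. For the primary outcome, add to section 3.3:

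1. A delta-adjusted multiple imputation that shifts the imputed log-odds of moderate-to-severe PPSP separately in each arm over a prespecified grid, including CBT-only shifts. Odds ratios of 1, 1.25, 1.5, 2 and 3 in each arm are one workable set; the team should fix its own before outcomes are compared by arm.
2. The tipping point: the combination of shifts at which the conclusion changes.
3. A reference-based run in which CBT participants lost to follow-up are imputed from the usual-care model. On the step 2 inputs this gives roughly (0.28 + 0.25 × 0.07)/0.35 = 0.85 at 25% missing and (0.28 + 0.35 × 0.07)/0.35 = 0.87 at 35%.

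In section 3.1, define early withdrawal as leaving follow-up, distinct from stopping CBT modules, and replace the conditional promise to account for it with a reference to this analysis.

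The cost is a few sentences of SAP text, a few extra runs of imputation code that is needed anyway, and possibly a less favourable statement about robustness.
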